probably around 30-40%, a sample of a total of 42 patients with NESIS seems justified. Then, considering that nearly a third of patients will have a NESIS score of less than 4 (non NESIS), 56 patients should be included in the study. Finally, given the number of refusals to participate in the study, probably nearly half of the patients, we plan to approach at least 120 patients.

The final recruitment target is therefore 56 patients (Figure 2).

Figure 2 – Patients distribution

Sample disponibility

The number of participants to be randomized is acceptable and feasible but will require a multi-center design. In fact, during the retrospective study at the CHUS from March 2016 to March 2018²⁸, 18 patients with TNS in the context of cSDH with negative EEGs were identified. Thus, considering at least 4 centers participating in the study, the inclusion of 56 patients in 3 years seems realistic. Moreover, the NESIS entity being newly recognized (mentioned only since 2018), the incidence of NESIS is probably higher than what was found between 2016-2018, the patients being now more easily identified and classified.

Patient recruitment

Patients will initially be identified by neurosurgeons and neurologists from participating centers. These physicians will be aware of the existence of our study and will have the list of inclusion and exclusion criteria. They will therefore be able to inform us when a potential candidate is hospitalized.

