These patients will then be seen during an initial visit by the research nurse. This meeting will take place during their hospitalization, in the patients' respective rooms or in a closed room (if multiple bed in the same room) (in order to avoid any external influence on the consent, in addition to better maintaining the confidentiality of the candidates). The purpose of this visit will be to assess the patient's eligibility for the study, to explain the purpose of the study and its interventions. If the patient wishes to participate in the study, a consent form will be read and signed by the patient (Appendix 2). The consent must meet the same criteria as what is applied in the clinic, or a patient must be able and offer free and informed consent. Substituted consent in the event of incapacity (permanent or temporary) with the most significant relative, at the bedside or by telephone will also be authorized. This form will contain the frequent and serious side effects of the two proposed treatments. All the patients who sign will be randomized in the study, into the TPM or LEV group. The method and location of recruitment will therefore be the same for all patients (intervention and active comparator).

Randomization will be made by random block allocation. A number will be assigned to each patient and will be entered into a software that will allow patient randomization, which can be found on the site: https://www.randomizer.at. Patients will be matched there for their NESIS scores (\geq 4 or <4), their home sites (CHUS or other centers) and the presence of SDH evacuating surgery (yes or no). These factors seem to us to be the ones that could have the greatest impact on the results. When starting the randomization, the software must be blocked in order to allow its use, so no modification of the randomization parameters can be added when the process is going to be started.

As recruitment and randomization take place during hospitalization of patients, no travel or additional testing will be required.

Sampling bias control

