Safety monitoring: Every month, from the time when 10 patients have been recruited, safety data (dropout, major side effects (requiring discontinuation of treatment) and persistence of neurological symptoms (yes or no)) will be compared in both groups. If a difference of more than 50% is identified for any of these data, the ethics committee will immediately **be** informed. A modification or discontinuation of the study will then be evaluated for reasons of safety, theoretical efficacy or futility.

Limitations of the study

Obviously, our study includes several sources of bias that we anticipate, however we will try to limit their impacts.

Selection bias

The patients who will be selected in our study may not represent the target population of our study. Indeed, a bias of voluntarism is inherent in the estimate of our study. Patients agreeing to participate in a study often do not have the same characteristics as those refusing, causing a gap between the study population and the target population. To limit the impact of this bias, we have designed our study so that it does not represent additional displacement or test for patients, in order to limit refusals to participate. In addition, the use of a non-probability sample can lead to a reference bias. Patients attending the coordinating center may differ from those attending another, for environmental, geographic or other reasons. To limit this bias, by using a multicenter study, we took several centers that are geographically distant, which will represent the general population more fairly. In addition, the recruitment being done in a similar way for the two groups and the matching according to the home hospitals will allow to balance these possible differences which could interfere during the recruitment.

Measurement bias

Some fluctuation in the measuring instrument (questionnaire) may occur. In fact, over time, the patient may find the questionnaire redundant and become bored, and therefore respond less well to it. To limit the impact of this factor, we have limited the number of follow-ups. In addition, in order to balance this fluctuation in the two groups, we will use the same questionnaires in both groups.

Compliance bias

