Because TPM causes more side effects than LEV, compliance in this group may be lower. To limit the impact of this bias, active monitoring will be carried out with patients in the event of significant side effects, in order to reduce the dose of their treatment. This will limit drop-outs, as well as encourage better compliance. Then, the antiepileptics will be introduced gradually, in order to limit the side effects which would lead to a decrease in compliance.

Desirability bias

Because patients will know with which antiepileptic drug they will be assigned to, they could involuntarily change their different responses during assessments. Indeed, they might be tempted to demonstrate that TPM, treatment intervention, is more effective than it actually is. The same goes for side effects, which might be exaggerated by a patient knowing to take TPM, which is known to cause more side effects. To limit this bias, with the agreement of the ethics committee, we will approach patients during consent in a non-nominal manner. Indeed, while explaining that the two treatments are as effective as each other in epilepsy, we will explain that we want to demonstrate whether there is superiority of one of the two drugs over the other. Our hypothesis considering TPM being more efficient would remain confidential especially as this remains hypothetical. In the same sense, upon consent, all possible side effects will be presented in the form of a list, not distinguishing which are found more with which antiepileptic. Thus, even knowing the antiepileptic medication prescribed, patients will not be able to influence their responses for or against a particular treatment, not knowing which characteristics belong to which treatment. The two groups will therefore have the same potential information regarding their antiepileptic drug.

Other limitations :

The effect of Leveracetam on cortical depolarizations remains conflicting, however, if present, it may lessen the impact of our results. In addition, the favorable natural course of cortical depolarizations could mask the significant difference between our two groups.

Time and personnel management

Initial and follow-up in-clinic assessments will be performed during regular hospital hours. Telephone assessments will be carried out during the day or evening by a member of the research team.

Ethics

Consent

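### The 50% safety trigger has no stated scale: as percentage points it usually misses a large excess, and as a ratio it fires on 1 event against 0

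*Protocol*

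**What the plan says.** The rule is in the Protocol under Oversight mechanism, in the paragraph on safety monitoring.

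- Timing: "Every month, from the time when 10 patients have been recruited".
- Items: "safety data (dropout, major side effects (requiring discontinuation of treatment) and persistence of neurological symptoms (yes or no)) will be compared in both groups".
- Trigger: "If a difference of more than 50% is identified for any of these data, the ethics committee will immediately" be informed. Modification or discontinuation of the study is then considered.

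The same section declines an independent monitoring committee and leaves monitoring to the project team. No scale, denominator, minimum count or reason is given for the 50%.

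Two other sections bear on it. Under Compliance bias: "Because TPM causes more side effects than LEV, compliance in this group may be lower". Under Sample size, dropout or loss to follow-up is put at "probably around 30-40" per cent, and the recruitment target is 56. Under Patient recruitment: "Randomization will be made by random block allocation". The allocation ratio is not stated.

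**The concern.** One fixed threshold is applied to two safety items, at 10 patients and at 56 alike. The same observed gap means little with 5 patients per arm and a great deal with 28. A fixed threshold therefore cannot suit both, and the reader cannot tell on which scale it lies.

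The protocol expects the topiramate (TPM) arm to tolerate treatment less well than the levetiracetam (LEV) arm. It has no independent committee, so this sentence is the only stated route by which a difference between the arms reaches the ethics committee. If the alert is too insensitive, a real excess of treatment-stopping side effects may not be reported outside the team. If it fires mostly by chance, its reports carry little information.

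The point concerns dropout and side effects requiring discontinuation. Whether symptom persistence belongs in a safety alarm is a separate matter.

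**Working it through.** **Inputs.** The target is 56 (Sample size), which reproduces as 30 × 1.40 = 42 and 42 × 4/3 = 56. Per arm this is 56/2 = 28, assuming 1:1; the equal targets of 15 per arm in the NESIS subgroup support that. Monitoring starts at 10 patients, so 5 per arm. The protocol states no event rates by arm for these two items, so the rates below are assumptions shown over a range. It also gives no performance figure for the trigger, so there is none to reproduce.

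Write x_T and x_L for the events on TPM and LEV among n per arm. The chance of an alert at one look is the sum of Bin(x_T; n, p_T) × Bin(x_L; n, p_L) over all pairs that fire. Over all looks, I take one look after each added pair from 5 to 28 per arm, which is 24 looks.

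**Percentage points: fires if |x_T − x_L| > n/2.**

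- At 28 per arm the gap must be at least 15 events. 14 v 0 is 50.0 points and does not fire (two-sided Fisher p = 0.000014); 15 v 0 does. By comparison, 6 v 0 already has p = 0.023.
- If LEV loses 30-40% of 28 (8 to 11 patients), TPM must lose 8 + 15 = 23 to 11 + 15 = 26, or 82-93%.
- At 5 per arm, 3 v 0 fires, although its two-sided Fisher p is 0.17.

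Worked example at 5 per arm, 40% v 5%: P(x_T ≥ 3)·P(x_L = 0) + P(x_T ≥ 4)·P(x_L = 1) + P(x_T = 5)·P(x_L = 2) = 0.317 × 0.774 + 0.087 × 0.204 + 0.010 × 0.021 = 0.26.

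| True rates 40% v 5% | 5 per arm | 10 | 14 | 28 | all looks |
|---|---|---|---|---|---|
| chance of alert | 26% | 12% | 10% | 5% | about 40% |

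**Ratio: fires if the higher count exceeds 1.5 times the lower (equal arms).** Both 1 v 0 and 2 v 1 fire. Even this reading has variants: taken relative to the higher count, 2 v 1 is exactly 50% and does not fire, while 1 v 0 still does.

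| Equal true rates in both arms | 5 per arm | 10 | 28 |
|---|---|---|---|
| 10% | 54% | 66% | 58% |
| 35% | 60% | 47% | 26% |

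Each entry is the false-alarm chance at a single look for one item.

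**A trigger that depends on n: one-sided Fisher exact p<0.05.** Against zero events, p = C(n, x)/C(2n, x).

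- 28 per arm: 4 v 0 gives 20,475/367,290 = 0.056 and 5 v 0 gives 98,280/3,819,816 = 0.026, so 5 v 0 fires.
- 5 per arm: 3 v 0 gives 10/120 = 0.083 and 4 v 0 gives 5/210 = 0.024, so 4 v 0 fires.
- For 40% v 5% it alerts in 92% at 28 per arm and about 95% over all looks.
- Either-arm false alarms over all looks, per item, are about 6% at equal rates of 10%, 14% at 20%, 17% at 30%, 18% at 35% and 19% at 40%. The present points reading gives about 9-12% at 30-40%.

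**The case against.** A reader might infer that the rule cannot detect harm, and that 14 of 28 stopping on TPM against 0 of 28 on LEV would never reach the ethics committee. The documents do not support that.

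- The example is silent only on the percentage-point reading, which the protocol does not state. As a ratio, 14 v 0 fires.
- It is silent only at a single look with 28 per arm, and it lies exactly on the boundary. Looks are monthly. If the 14 events are placed at random among the 28 TPM patients, with none on LEV, about 90% of orderings exceed 50 points at an earlier look (about 82% if looks come only at every third pair). Late reporting of events would lower these figures.
- On the points reading the rule is weak, not blind. Over all looks it fires in about 40% for 40% v 5%, 55% for 50% v 10% and 80% for 60% v 10%.
- The alert becomes less likely as patients accrue only when the true gap is below 50 points.

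Two further points are fair. Individual patients are protected separately, through dose reduction or stopping for side effects and active monitoring. The team also compares the arms every month whether or not the trigger fires. And a Fisher test is only one of several reasonable triggers.

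All of this stands, and it limits the claim to a badly specified alert. It does not rescue the rule: the scale is still undefined, and each reading performs badly when followed.

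**Conclusion.** The concern holds in this form: the trigger has no stated scale or denominator, and neither reading works for dropout or treatment-stopping side effects. As percentage points it misses a true 40% v 5% excess in about 60% of trials over all looks (100 − 40), and in 95% at a single look with 28 per arm. As a ratio above 1.5 it gives a false alarm in roughly a quarter to two thirds of single looks when the arms are equal.

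This is more than detail left for a later document, because the protocol fixes the rule and fixes it badly. The figures rest on 1:1 allocation, full recruitment, events known at once, a look after every added pair and the assumed rates. Fewer looks or delayed reporting would lower the all-looks figures. The protocol should be changed, since this is its only between-group route to the ethics committee and it expects worse tolerability on TPM. The evidence does not show that a serious imbalance would go unreported to the end of the trial.

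**What to change.** In the safety-monitoring paragraph, for dropout and for side effects requiring discontinuation:

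1. State the scale and the denominator, for example all patients randomised to date in each arm.
2. Replace the 50% with a trigger that takes account of the number of patients. One example is to inform the ethics committee when a monthly one-sided Fisher exact test for an excess in either arm gives p<0.05, and to report the counts.
3. State that the trigger informs the committee and is not a stopping rule.
4. State the scale for the symptom-persistence item as well, so that the sentence is not left half defined.

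The edit is a few sentences. Testing each direction at one-sided 0.05 is nominally a two-sided 10% test at every look, so chance alerts increase: about 6-14% per item over all looks at equal rates of 10-20%, and 17-19% at the expected 30-40% dropout, against about 9-12% there under the present points reading. Each costs one report. At the first look the example is also stricter than the points reading (4 v 0 instead of 3 v 0 with 5 per arm). A sponsor who prefers another threshold should give its alert and false-alarm rates in the same way.

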Appendix

Appendix 1 – NESIS score

NESIS	Valeur des points pour le calcul du score	
Features supporting NESIS		
Negative symptoms	+4	
Duration of ≥ 5 min	+3	
Dysphasi a	+3	
Migration	+1	
≥ 5 episodes	+1	
Stereotypy	+1	
Characteristics against NESIS		
Altered state of consciousness	-4	
Clonic movements	-4	
Diagnosis of NESIS if total score ≥ 4 and no positive EEG		

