All adult patients presenting to any of the participating centers with transient neurologic symptoms in the setting of cSDH. The study will be multi-center and Sherbrooke will be the coordinating center.

Patients selection – sampling

- All patients presenting to one of the participating centers with transient neurological symptoms in the context of cSDH.
- Convenience non-probability sampling.
- Systematic sampling, recruiting all patients presenting at one of the participating centers, regardless of the time of admission (night, weekend). As all patients presenting with TNS in the setting of cSDH will be eligible for the study, the sample should be representative of the population. Of course, they will be included according to their willingness to participate in the study, so a bias of voluntarism is unmissable.

Inclusion criteria

- ≥ 18 years old
- Chronic subdural hematoma
- Transient neurological symptoms (Sensory, motor, cerebellar or speech symptoms, lasting 6 hours or less)
- Initial negative EEG

Exclusion criteria

- Contraindications to Levetiracetam
 - Psychiatric history (major depression, psychosis, risk of suicide)
 - History of hypersensitivity to LEV (anaphylaxis, angioedema, skin reaction)
- Contraindications to Topiramate
 - History of hypersensitivity to TPM
 - o Glaucoma
 - Past nephrolithiasis
- Known epilepsy or seizure before the current subdural hemorrhage
- Actual take of antiepileptic
- Intracranial pathology not caused by SDH (intra-parenchymal hemorrhage, neoplasia)
- Pregnancy or planning to be

- Inability to carry out the necessary follow-ups for the study
- Refusal of the attending physician

Sample size

The studies directly concerning our subject being few or even zero, we decided to calculate our sample size based on two calculations and two types of data (which do not perfectly represent our variables, each in their own way) in order to optimize our chances of obtaining a size approaching the one we need for adequate power.

Based on the means and standard deviations of reduction in cortical depressions with TPM and LEV in the fundamental studies previously described^{24,25}, it is possible for us to calculate the sample size that should allow us to establish a significant difference between our groups, if possible.

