First, several demographic and characteristic data regarding subdural hematomas and transient neurological symptoms will be collected. These data will allow us to assess whether certain factors have an impact on the response to treatment.

Demographic data	Age	
0.1	Sex	
	Dominant hand (right or left)	
Life habits	Tobacco	
	Alcohol	
	Drugs	
Comorbidity	High blood pressure	
	Diabetes (with or without insulin)	
	Dyslipidemia	
	Auricular fibrillation	
	Coronary disease	
	Peripheric vascular disease	
	Migraines (with or without aura)	
Past medical history	Stroke, transient ischemic attack	
	SDH	
	Cranial lesion	
	Cranial surgery	
Drugs	Antiplatelet	
	Anticoagulant	
	Beta-blocker	
	Magnesium	
SDH type (Nakaguchi	Homogeneous	
classification)	Laminaria	
	Separated	
	Trabecular	
SDH location	Right	
	Left	
	Both	
SDH cause	Traumatic (light, moderate, hard)	
	Autre	
SDH thickness	Millimeters	

Table 1 - Demographic data and characterization of subdural hematoma

Middle line shift	Millimeters
Initial Glasgow score	3-15
Draining surgery	Yes
	No
Surgery location	Right
	Left
	Both
Concomitant subarachnoid	Yes
hemorrhage	No
Electrocorticography	Yes
	No
MRI	Yes
	No
	Particularities

Table 2 – TNS characteristics

Visual symptoms	Visual loss	
	Twinkling light	
	Other	
Sensory symptoms	Hypoaesthesia	
	Paresthesias	
	Other	
Motor symptoms	Paresis	
	Clonies	
	Change in tone	
	Other	
Speech symptoms	Aphasia	
	Dysarthria	
	Mutism	
	Other	
Cerebellar symptoms	Balance disorder	
	Nausea and vomiting	
	Dizziness / Vertigo	
	Other	
Altered state of consciousness	Yes or No	
Duration of symptoms	Minutes	
Number of episodes		
Migration of symptoms	Yes or No	
Stereotyped symptoms	Yes or No	
Prodrome	Туре	
Postictal	Yes or No	
NESIS score at randomization	-8 à 13	

Variables

Research question: Is Topiramate more effective than Levetiracetam in patients with TNS and negative EEG in the context of SDH, in the NESIS group (increased probability of cortical depolarization), compared to the non-NESIS group (increased likelihood of epilepsy) ?

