The existence of propagated cortical depolarizations will be assessed by electrocorticography (ECoG) for some operated patients (see below for the detailed procedure) as well as by a surface EEG and a near infrared spectroscopy monitor. These paraclinical examinations will help to rule out a diagnosis of epilepsy and will provide the physiological data necessary for the confirmation of cortical depolarizations.

Side effects will be assessed and graded using CTCAE terminology (Common Terminology Criteria for Adverse Events)³¹.

After a first negative pre-randomization EEG, 2 more EEGs will be performed at 24 hour intervals in order to increase the diagnostic sensitivity of ictal activity. If an EEG is positive, there will be no further EEG. These EEG results will help for further validation of the NESIS score.

Magnetic resonance imaging will be recommended in patients with 3 negative EEGs, in order to rule out another structural cause, such as transient ischemic events. This will remain at the discretion of the clinician, depending on clinical relevance and availability of the examination..

Process

Initial meeting

Patients will be seen during their initial hospitalization following the diagnosis of TNS and their first negative EEG. If SDH evacuating surgery is planned for a patient who has already been randomized, they will be offered the installation of an ECoG monitor during the same surgery. This step will be optional. Subsequently, the patients will be reviewed postoperatively and the intervention will be started if transient neurological symptoms persist.

The meeting will be conducted by a research nurse or a member of the research team. An explanation of the study, drugs, goals, and intended patient involvement will be discussed. At this point, patients will have the choice of whether or not to sign the consent form. They will be given time for reflection, if desired. If the patient is participating in the study, demographic data, clinical characteristics of the subdural hematoma and characteristics of transient neurological symptoms will be collected using a standardized questionnaire (Appendix 3). Thereafter, treatment (TPM or LEV) will be assigned by randomization and started during hospitalization with a planned increase up to

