therapeutic doses according to the protocol below. A notebook containing the information discussed, the contact information and forms (appendix 5) for weekly monitoring of neurological symptoms and side effects will be given.

In parallel, after starting the treatment (TPM or LEV), two other daily EEGs will be performed. If an EEG is positive, there will be no further EEG needed. Additionally, if an EEG is positive, the patient will remain in the same treatment group, however, a subanalysis may compare the correlation between EEG and NESIS score results. In addition, brain magnetic resonance imaging will be recommended for patients with three negative EEGs to rule out an alternative diagnosis, such as transient ischemic events. This test is already part of the usual assessment of transient neurological symptoms with negative EEG and therefore does not represent an additional test for patients. However, this examination will be at the discretion of the clinician, depending on the clinical relevance and availability of the examination.

Electrocorticography

If the patient has TNS preoperatively, the installation of electrocorticography electrodes in the subdural space will be suggested. We anticipate that approximately 5 to 10 patients out of the 56 enrolled will be eligible and be offered this option. This step is optional and will not influence subsequent medical treatment. However, it will help to demonstrate the existence of propagated cortical depolarizations and potentially prove the effectiveness of a non-invasive screening strategy. If the patient agrees, two ECoG strip electrodes will be inserted into the subdural space along with the installation of the subdural drain during the surgery. The electrodes will be located at the level of the upper temporal line and oriented anteroposterior in order to cover the frontal operculum as well as the inferior parietal lobule. This procedure is identical to that carried out routinely in the surgical assessment of patients with epilepsy. The patient will then be transferred to the EEG monitoring unit where a surface EEG and a bi-frontal near infrared spectroscopy monitor will be installed. The patient will then be monitored continuously until at least 5 episodes of TNS are recorded, or for a maximum of 72 hours. The electrodes will then be removed by traction at the bedside and a stitch will be performed under local anesthesia. The data will be analyzed by an epileptologist.

Intervention

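### The undated EEG clause in Appendix 1 conflicts with the randomised NESIS stratum and, read literally, lets on-treatment EEGs redraw the primary subgroup

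*Protocol*

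**What the plan says.** The protocol describes NESIS membership in several places.

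- **Appendix 1 (NESIS score):** "Diagnosis of NESIS if total score ≥ 4 and no positive EEG". It does not say which EEG counts or up to when.
- **Inclusion criteria:** "Initial negative EEG".
- **Patient recruitment:** "Patients will be matched there for their NESIS scores", split at 4, along with site and evacuating surgery. EEG is not part of the stratification.
- **Table 2 (TNS characteristics):** the recorded variable is "NESIS score at randomization".
- **Sample size:** "nearly a third of patients will have a NESIS score of less than 4 (non NESIS"), which uses the score with no EEG condition. The same section sizes the trial on the NESIS subgroup and places non-NESIS patients outside the primary outcome.
- **Measuring instrument:** "After a first negative pre-randomization EEG, 2 more EEGs will be performed at 24 hour intervals". The results are meant to help validate the score.
- **Initial meeting:** "after starting the treatment (TPM or LEV), two other daily EEGs will be performed". Further, "if an EEG is positive, the patient will remain in the same treatment group", and a sub-analysis may relate EEG results to the score. The NESIS subgroup is not mentioned.
- **Statistics:** the analysis is by intention to treat. The primary comparison is described for symptoms with a negative EEG, without saying which EEG.

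**The concern.** The primary objective concerns patients with a positive NESIS score, so membership of that subgroup decides who enters the primary comparison. A patient with score ≥ 4 and a positive second or third EEG has two statuses. By the randomisation stratum the patient is NESIS; by the closing line of Appendix 1 the patient is not.

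If Appendix 1 is applied, randomised patients leave the primary comparison because of a measurement made on topiramate or levetiracetam. Both are anticonvulsants, so the chance of a positive EEG on treatment may differ by arm. The patients left in each arm would then no longer be comparable by virtue of randomisation, and the analysis would not be by intention to treat. The planned comparisons of each drug's response between NESIS and non-NESIS patients would be affected as well.

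**Working it through.** **1. What the primary comparison rests on.** The protocol's proportions formula reproduces: 4 × (1.960 + 1.282)² × 0.57 × 0.43 / (0.14 − 1)² = 13.93, so 14 in total and 7 per arm. The protocol raises this by judgement to 15 per arm, or 30 NESIS patients analysed. At 15 per arm one patient is worth 1/15 = 6.7 percentage points. None of this depends on which NESIS definition is used.

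**2. The two definitions side by side.**

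| Randomised patient (entry EEG negative) | Randomisation stratum | Appendix 1, read literally |
|---|---|---|
| Score ≥ 4, later EEGs negative | NESIS | NESIS |
| Score ≥ 4, second or third EEG positive | NESIS | not NESIS |
| Score < 4 | non-NESIS | not NESIS |

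On the day of randomisation the two agree for everyone, because the entry EEG is negative by inclusion criterion. They can part only in the second row, and only on EEGs recorded after treatment has started.

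**3. How many patients.** The documents give no rate of later positive EEGs. With assumed rates of 5%, 10% and 20% among patients with score ≥ 4:
- of 42 enrolled: 2.1, 4.2 and 8.4;
- of 30 analysed: 1.5, 3 and 6.

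Two indirect figures suggest that the number may be small.
- *Reported accuracy.* The introduction gives 100% specificity for a score ≥ 4. If this means none of 20 or none of 39 patients (assumption: one of the two groups reported there), the upper 95% limits are 1 − 0.025^(1/20) = 16.8% and 1 − 0.025^(1/39) = 9.0%. These limit the share of EEG-positive patients who score ≥ 4. That is related to the share of high scorers who later turn positive, but it is not the same quantity.
- *Pilot.* The protocol reports 13 of 22 patients with score ≥ 4 (59%), 18 patients with negative EEG, and a NESIS share of 72%. Since 13/18 = 72%, the figures fit none of the 13 having had a positive EEG. That is an inference. The upper limit for 0 of 13 is 1 − 0.025^(1/13) = 25%.

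**4. What removal could do to the comparison.** All inputs here are assumed except the 14%, which is the protocol's comparator rate. Let a share q of score ≥ 4 patients have epilepsy and all resolve. Let the rest resolve at 14% on either drug, so that there is no true drug difference. Let a fraction d of the epilepsy patients in an arm show a later positive EEG and be removed. The resolution rate in that arm becomes

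[q(1 − d) + 0.14(1 − q)] / [q(1 − d) + (1 − q)].

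- Equal d in both arms: the difference is 0.
- d = 20% in one arm and 60% in the other, q = 10%: (0.08 + 0.126)/0.98 = 21.0% against (0.04 + 0.126)/0.94 = 17.7%, a spurious difference of about 3 points.
- Same d, q = 5%, 20% and 30%: about 2, 7 and 9 points.

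The arm with fewer positive EEGs is favoured. Exchanging the two values of d reverses the sign.

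**The case against.** The strongest reply is that the protocol never applies the closing line of Appendix 1 to the analysis. The introduction cites the appendix only for the score, and the score was built in a cohort that included EEG-positive patients, so the EEG clause has an ordinary purpose there. Where the trial's own groups are set, the text mostly uses the score alone, and Table 2 dates it at randomisation. Later EEGs are assigned to validating the score, which would be circular if the same EEGs redefined the group. The Statistics section commits to intention to treat. The later EEGs are also daily from the start of treatment, before the first weekly dose increase, which leaves little time for a difference between the drugs. Finally, a SAP could settle the matter.

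Most of this stands. A reader might infer that the sponsor plans to reclassify patients after treatment starts. The documents do not support that; score at randomisation is the likely intention.

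The conflict nevertheless remains. The only formal statement of what counts as NESIS carries an undated EEG condition. The sentence on later positive EEGs protects the treatment group and is silent on the subgroup. The negative-EEG wording in Statistics is undated too. This is a stated definition that disagrees with the randomised stratum, and so more than a detail left to a SAP.

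**Conclusion.** The point holds as an unresolved contradiction about who belongs to the primary subgroup. Taken literally, Appendix 1 would let EEGs recorded on study drug remove randomised patients from the primary comparison, contrary to intention to treat.

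The size is unknown. Few patients may be affected, though with 15 per arm even one or two would be visible in the result. The 2 to 9 points in the working illustrate a mechanism under an assumed imbalance between arms; they do not estimate its effect in this trial.

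A reader might go further and infer that the definition inflates the apparent benefit of topiramate, because patients with probable epilepsy respond to standard drugs and their removal would lower the levetiracetam rate. The documents do not support this. It looks at one arm only, it needs a count of later positive EEGs that the protocol does not give, and removal acts in both arms. Any net effect depends on which drug shows more positive EEGs. The protocol does not say, and it describes the two drugs as comparable for seizure control.

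**What to change.** State in Appendix 1 and in the Statistics section that, for all treatment comparisons, NESIS means a score of 4 or more at randomisation with a negative entry EEG (the randomised stratum), and that later EEG results do not change it. In Statistics, also say that the negative EEG in the primary outcome is the entry EEG. Use the second and third EEGs only in the score-validation sub-analysis that the Measuring instrument and Initial meeting sections already describe.

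The cost is a sentence or two in two places. No new data, change in sample size or change in patient care is needed. A few patients with a later positive EEG would stay in the NESIS group and may slightly dilute the contrast. The wording should be settled before outcomes by arm are seen; under Safety monitoring the project team compares symptom persistence between groups every month once 10 patients have been recruited.
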